8.2. Secondary Efficacy Endpoint(s) and Analyses

8.2.1. Time to conversion from AF from start of infusion

The time to conversion from AF from start of infusion will be analysed using Kaplan-Meier methods. The number of patients that reached cardiac conversion within 90 mins of start of study drug infusion will be summarized using the median time to cardiac conversion along with the interquartile range (IQR).

A Kaplan Meir plot stratified by treatment group will be presented. A logrank test will be used to compare treatment groups.

Time to conversion (in min) will be calculated using the formulae:

This document is confidential.

Time to conversion (in min) = (Time of conversion or censoring - time of start of infusion).

In case of AF persistence at 90 min after start of infusion, a direct-current (DC) electrical cardioversion is to be done within 180 min post-infusion start. Patients who have electrical cardioversion will be censored. The time of censoring will be 90 min.

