Secondary endpoints relating to proportions will be analysed using a logistic regression model in a similar manner to that of the primary endpoint. Time to conversion will be analysed using Kaplan-Meier methods and, if met, the median time to conversion will be presented, along with the corresponding Kaplan-Meier plot stratified by treatment group.

Full details of all statistical analyses will be provided in the SAP.

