APPENDIX I SAMPLE SAS CODE IN STATISTICAL ANALYSIS

1) Sample Code for Efficacy Analysis

The logistic regression will be used to analyze all efficacy endpoints relating to proportions

The following is an example of the SAS codes used to perform the analysis of this LOGISTIC model.

* SAS Codes: *LOGISTIC* model

* Variables in the model:

* resp = proportion of patients who have converted from AF within 90 mn from the start of infusion

* Duration of current AF episode = Dur

*trtp = treatment planned

*****;

```
proc logistic data=eff descending;
class trtp (param=ref ref='Placebo');
model resp (event="Yes")= trtp dur;
```

```
contrast 'Pairwise' trt 1 -1 0 /estimate=exp;
contrast 'Pairwise' trt 1 0 -1 /estimate=exp;
```

```
ods output Contrastestimate=est;
run;
```

A Kaplan-Meier analysis was used for time to conversion. An example of the SAS code to perform this analysis is below.

* SAS Code: Kaplan-Meier Analysis

* Variables in the model:

* timeconv = The time to conversion from AF from start of infusion

* Censor = censor variable (0=patients with conversion, 1=censored patients, no pharmacological conversion)

*trtp = treatment planned

*****;

```
proc lifetest data=dataset plot;
```

This document is confidential.

```
time timeconv*censor(1);
strata trtp/ test=(logrank) diff=control('Placebo');
ods output quartiles/quartile
run;
```

2) Sample Code for graph

```
*****
```

* SAS Code: Graph Concentration response relationship:

QTcF versus AP30663 plasma concentrations

* PCTRESN = Plasma concentration

* AVAL = QTcF

```
*****
```

```
proc sgplot data=PKPD;
reg x=PCSTRESN y=AVAL /CLM alpha=.05;
refline 0/axis=y;
label PCSTRESN="Plasma concentration (unit)";
run;
```

This document is confidential.

AP30663_2001_SAP_Text_4.0_20Feb2023

Final Audit Report

2023-02-20

Created: 2023-02-20

By: PPD [REDACTED]

Status: Signed

Transaction ID: PPD [REDACTED]

"AP30663_2001_SAP_Text_4.0_20Feb2023" History

-  Document created by PPD [REDACTED]
2023-02-20 - 2:01:32 PM GMT- IP address: PPD [REDACTED]
-  Signer PPD [REDACTED] entered name at signing as PPD [REDACTED]
2023-02-20 - 2:04:32 PM GMT- IP address: PPD [REDACTED]
-  PPD [REDACTED] verified identity with Adobe Acrobat Sign authentication
2023-02-20 - 2:04:34 PM GMT
-  Document e-signed by PPD [REDACTED]
Signing reason: I am the author
Signature Date: 2023-02-20 - 2:04:34 PM GMT - Time Source: server- IP address: PPD [REDACTED]
-  Document emailed to PPD [REDACTED] for signature

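### At the protocol's example conversion rates, the planned median and IQR give no numerical time-to-conversion comparison with placebo, and the SAP 8.2.1 sentence conflicts with the SAP's own code

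*SAP*

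**What the plan says.** SAP 8.2.1 opens: "The time to conversion from AF from start of infusion will be analysed using Kaplan-Meier methods". Its next sentence takes as its subject "The number of patients that reached cardiac conversion within 90 mins of start of study drug infusion" and says this "will be summarized using the median time to cardiac conversion along with the interquartile range (IQR"). A Kaplan-Meier plot by treatment and a log-rank test follow. On censoring: "Patients who have electrical cardioversion will be censored. The time of censoring will be 90 min".

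Appendix I codes the censoring variable as "0=patients with conversion, 1=censored patients, no pharmacological conversion", so every patient without pharmacological conversion is in the risk set. It runs PROC LIFETEST by planned treatment and saves the quartiles ("ods output quartiles/quartile"). Table 14.2.2.1.1 is titled as a Kaplan-Meier analysis on the Full Analysis Set.

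Protocol 11.1.3 is more guarded: "if met, the median time to conversion will be presented". It does not mention an IQR. The SAP drops the condition, adds the IQR, and lists no changes from the protocol in its section 12.

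**The concern.** A quartile that the curve does not reach by 90 min cannot be estimated. If the placebo curve reaches none, neither the median nor the IQR can be compared with placebo. What remains is a p-value and a picture, and neither says how much sooner patients convert on drug. The protocol's condition allows for a missing median but names no substitute.

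Interim reporting is affected too. The SAP's indexes mark Table 14.2.2.1.1 for delivery to the DMC but not the Kaplan-Meier figure (14.2.2.1.3), so the DMC would see the quartiles without the curve.

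The wording is a second, smaller problem. A median among converters can be computed in any arm with a converter, so a programmer who finds the placebo quartiles missing could turn to it. It compares groups selected by outcome.

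**Working it through.** **Inputs.** Final data of Examples 1-4 in protocol 17.3; the 0.65 benchmark and 0.90 closing rule (protocol 11.1.6, SAP 11); the 90-min censoring rule (SAP 8.2.1).

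**The plan's own figures.** With the Beta(1+x, 1+n-x) posterior, 28/36 gives Pr(P>0.65) = 0.941 (protocol: 0.94) and 19/24 gives 0.917 (protocol: 0.91). The example counts are read correctly.

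**Which quartiles exist.** If all conversions occur by 90 min and everyone else is censored at 90 min, the Kaplan-Meier estimate satisfies 1 - S(90) = x/n. The lower quartile, median and upper quartile need x/n to reach 0.25, 0.50 and 0.75.

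| Example | Placebo | Active arms |
|---|---|---|
| 1 | 6/42 = 0.143 | 3 mg/kg 10/18 = 0.556; 4 mg/kg 8/12 = 0.667; 5 mg/kg 28/36 = 0.778 |
| 2 | 8/42 = 0.190 | 3 mg/kg 4/18 = 0.222; 5 mg/kg 5/12 = 0.417; 6 mg/kg 24/36 = 0.667 |
| 3 | 8/42 = 0.190 | 3 mg/kg 9/18 = 0.500; 4 mg/kg 16/24 = 0.667; 5 mg/kg 19/24 = 0.792 |
| 4 | 6/42 = 0.143 | 2 mg/kg 4/12 = 0.333; 3 mg/kg 13/18 = 0.722; 5 mg/kg 24/36 = 0.667 |

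- Lower quartile: 11 of 16 arms.
- Median: 8 of 16, or 9 if 9/18, exactly on 0.50, is counted.
- Upper quartile, hence full IQR: 2 of 16 (28/36 and 19/24).
- Placebo: none of the three in any example.

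Example 4's 13/18 is carried forward from Part 1. It is not printed in that example's final row, but the posterior row at 108 patients and the conclusion both include that dose. Printed cells alone give 2 of 15.

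**How certain this is for placebo.** The maximum placebo size is 18 + 72/3 = 42; at the first Part 2 interim it is 18 + 18/3 = 24. The lower quartile needs 11/42 or 6/24. Binomial tail probabilities at true rates of 0.14 and 0.19:
- n = 42: 0.03 and 0.16.
- n = 24: 0.11 and 0.30.

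The median needs 21/42 or 12/24; the probability is below 0.001 in all four cases.

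**Active arms at a true rate of 0.65.** Probability that the upper quartile is reached:

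| n | Conversions needed | Probability |
|---|---|---|
| 12 | 9 | 0.35 |
| 18 | 14 | 0.19 |
| 24 | 18 | 0.21 |
| 36 | 27 | 0.14 |

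These probabilities count an arm exactly on the boundary as reaching the quartile, which favours the plan.

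**Doses closed for efficacy.** The smallest counts with Pr(P>0.65) at or above 0.90 are 11/12, 15/18, 19/24, 28/36 and 36/48, that is 0.917, 0.833, 0.792, 0.778 and 0.750. All reach 75%, the last exactly.

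**What a converters-only median would show (assumed hazards).** Let p be conversion by 90 min. With constant hazard L = -ln(1-p)/90, the converters' median is -ln(1-p/2)/L and the restricted mean is p/L. With p = 0.14 on placebo and 0.56 on drug:
- Converters' medians: 43.3 and 36.0 min, a gap of about 7 min.
- Restricted means: 83.5 and 61.4 min, a gap of about 22 min.

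If the drug conversions are instead spread evenly over the 30-min infusion, the converters' median is 15 min and the restricted mean is 0.56 x 15 + 0.44 x 90 = 48.0 min. The gaps become about 28 and 36 min.

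**The case against.** The strongest reply is that 'not reached' is a normal and informative Kaplan-Meier result. The protocol foresees it for the median, the curve shows conversion at every time, and the 90-min proportion is already the primary endpoint with its own analyses. All of this stands. It limits the importance of the point but does not supply a time-based effect estimate.

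Four stronger readings are tempting, and the documents do not support them.

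- *The SAP plans a converters-only median.* The sentence can be read that way, but the section names Kaplan-Meier methods, its time formula includes censoring times, the code includes non-converters, and the table is on the Full Analysis Set. This is a conflict of wording, and the weight of the text favours all patients.
- *A converters-only median would hide most of the effect.* That depends on the assumed hazard. Under a constant hazard it shows about 7 of 22 min; with conversions confined to the infusion, about 28 of 36. The documents do not fix the shape.
- *No placebo quartile can exist.* That is true of every example, but protocol 17.3 offers the examples to clarify the design rules, not as forecasts. A placebo lower quartile is possible, with the probabilities above. The examples also count responders free of recurrence for 1 min. If briefer conversions count as events here, rates could be a little higher, although placebo would need 11 - 8 = 3 to 11 - 6 = 5 more conversions out of 42.
- *Upper quartiles are missing even for a successful dose.* The 65% rate is a threshold to exceed, and a dose closed for efficacy at the sizes listed above does reach its upper quartile.

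**Conclusion.** The point holds as a modest one about a secondary endpoint. At placebo rates of 14-19% the placebo median is effectively unreachable and the lower quartile usually is not reached. The full IQR exists in 2 of 16 example arms, and at a true 65% the upper quartile is reached with probability only 0.14-0.35 for arms of 12-36. The planned outputs therefore contain no numerical time-based comparison of a dose with placebo.

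This rests on two assumptions: that real rates resemble the examples, and that all non-converters are censored at 90 min. The code comment says the latter; the text of 8.2.1 literally censors only patients who have electrical cardioversion. The conclusion does not depend on the constant-hazard illustration.

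The log-rank test, the plot, the interim dose rules and the primary superiority conclusion do not use the median or IQR and are unaffected.

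**What to change.** In SAP 8.2.1 and Table 14.2.2.1.1, for the whole Full Analysis Set:

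1. Report the restricted mean time to conversion over 0-90 min by arm, with the dose-minus-placebo difference and 95% CI. Where nobody is censored before 90 min, this is the arm average of the smaller of conversion time and 90 min.
2. Report Kaplan-Meier cumulative conversion at fixed times, for example 30, 60 and 90 min, with 95% CI. The 90-min value nearly repeats the primary endpoint; the earlier times add the information on speed.
3. Keep the log-rank test and the Kaplan-Meier quartiles, printed as 'not reached' where that applies.
4. Reword the sentence so that the median and IQR are the all-patient Kaplan-Meier quartiles, and state that no converters-only median is used to compare arms. Align the censoring text with the code comment.

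The cost is a wording change and a few more output lines for a secondary endpoint. The data are already collected.

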8.4.8.2 Rescue Medication

All patients who will not convert from AF during infusion of the study drug or within 90 min after the infusion start should undergo DC electrical cardioversion within 180 min from the time the infusion started. DC electrical cardioversion should be performed using biphasic synchronised cardioverter with energy of 200 J.

All medications necessary for direct-current electrical cardioversion (e.g. sedatives) should be administered per local standards, observing limitations from [Section 8.4.8.1](#) (Prohibited Medication and Procedures), and should be recorded as concomitant medications.

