10.1 Efficacy, Pharmacokinetics, and Safety Measurements

10.1.1 Efficacy Variables

10.1.1.1 Holter Recording

ECG assessments for primary efficacy endpoint will be based on Holter ECG. Conversion from AF will be determined by the investigator and documented with a rhythm strip confirming conversion; time of conversion will be recorded in minutes after start of infusion.

In addition, the Holter will record ECG continuously and detect conversion from AF as well as monitor sustainability of the rhythm after conversion. The 12-lead Holter monitoring equipment will be centrally provided by Clario. Analysis of the primary and secondary efficacy endpoints will be based on Holter ECG and ECGs collected by the site. The Holter ECG recording will be initiated 30 min before the planned start of study drug infusion and will be continued for at least 8 h until after the last PK sampling on Day 1. Records will be available for assessment by the DMC at the IAs, will be used for the analysis of the primary and secondary efficacy endpoints, and may be further used for retrospective safety analyses ([Section 10.1.3.5](#)).

The following measurements will be provided for all ECGs extracted from the Holter recording: RR, PR, QRS, QT, QTcF, QTcB (optional), heart rate, T- and U- wave morphology classifications.

Triplicate ECGs will be extracted at the same time points as PK sampling except the 24h PK sampling (see Schedule of Assessments in [Section 8.1.2](#)) and will be read in a semi-automated manner by a blinded cardiologist. The arithmetic mean of the replicate values was used as the value for that time point.

The ECG laboratory processes all ECGs to produce regulatory-ready research data with all ECG interval duration measurement quality control and quality assurance processes completed on a continuing basis according to ERT's quality assurance guidelines and standard operating procedures (SOPs).

Central reading in the ECG core laboratory adheres to the following principles:

- The actual times of dosing, extraction windows, and PK sampling are communicated to the central ECG laboratory by the site.

- The central ECG laboratory identifies periods of stable heart rate on the continuous 12-lead ECG tracing within the 3-minute extraction window.
- Review of ECGs from a particular patient is performed by a single reader.
- Baseline and on-treatment ECGs are based on the same lead ECGs from a single patient.

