4.2. Secondary Efficacy Endpoints

- The time to conversion from AF from start of infusion.
- The proportion of patients with relapse of AF within 5 min (IRAF) following pharmacological or direct-current (DC) cardioversion.
- The proportion of patients in SR at $3\text{ h} \pm 1\text{ h}$ after start of infusion.
- The proportion of patients in SR at $24\text{ h} \pm 2\text{ h}$ after start of infusion.
- The proportion of patients in SR at $30\text{ days} \pm 5\text{ days}$ after start of infusion.

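### SAP 8.2.1 takes electrically cardioverted patients out of the risk set at 90 min but sets no 90 min limit on events, so one later unshocked conversion can produce a misleading Kaplan-Meier median or quartile

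*SAP*

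**What the plan says.** - **Endpoint.** SAP 4.2 defines it as "The time to conversion from AF from start of infusion", with no 90 min limit. The primary endpoint in SAP 4.1 does have one.
- **Time variable.** SAP 8.2.1 computes "Time of conversion or censoring - time of start of infusion", with no upper bound.
- **Censoring.** The only rule, also in 8.2.1, is "Patients who have electrical cardioversion will be censored. The time of censoring will be 90 min".
- **Event coding.** SAP Appendix I defines the censor variable as "0=patients with conversion, 1=censored patients, no pharmacological conversion". It has no 90 min condition. In the same appendix, the response variable for the logistic model does carry the 90 min limit.
- **Shock window.** Protocol 8.4.8.2 says patients still in AF "should undergo DC electrical cardioversion within 180 min from the time the infusion started".
- **Observation after 90 min.** Under Protocol 10.1.1.1 the Holter runs for at least 8 h and "time of conversion will be recorded in minutes after start of infusion".
- **Reported statistics.** Protocol 11.1.3 says "if met, the median time to conversion will be presented". SAP 8.2.1 adds the interquartile range, a plot by treatment group and a log-rank test. Its sentence on the median and interquartile range refers to patients who converted by 90 min.
- **Delivery.** SAP section 16 marks the Full Analysis Set Kaplan-Meier table for the interim analyses. SAP section 17 does not mark the figure.

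**The concern.** The two kinds of patient still in AF at 90 min are treated on different clocks. A shocked patient stops contributing at 90 min, even if still in AF at 120 min and not shocked until later. A patient who converts unshocked at 120 min is counted at 120 min. The late event is then divided by a risk set that omits patients who were in fact still in AF at that moment.

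Both the median and the quartiles are exposed. In an arm with fewer than half converted by 90 min, the right report is that the median was not reached, and the protocol's wording allows for that. The literal rule could print a number instead. The protocol's own examples put placebo at 10% to 20%, so placebo is the arm most open to this.

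**Working it through.** The documents state no expected median, event count or power for this endpoint, so there is no plan figure to reproduce. The check applies the literal rule to the protocol's example arms.

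**Inputs from the documents.** Conversions by 90 min in Protocol 17.3, Example 1: placebo 6/42, Dose 3 10/18, Dose 5 28/36. Example 2: placebo 8/42, Dose 5 5/12.

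**Assumptions.** Conversions before 90 min are evenly spaced from 10 to 80 min. One further patient converts unshocked at 120 min. All other non-converters are shocked and so censored at 90 min.

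**Formula.** The product-limit estimate S(t) is the product of (1 − d/n) over event times. Here d is the number of events and n the number at risk. With no censoring before 90 min, S(90) is the proportion not converted. At 120 min the late converter is alone at risk, so S is multiplied by 1 − 1/1 = 0.

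| Arm (Example 1) | S(90) | S after 120 min | Reported under the literal rule | Reported with everyone cut off at 90 min |
|---|---|---|---|---|
| Placebo 6/42 | 36/42 = 0.857 | 0 | median and both quartiles 120 min, with 7/42 = 17% converted | none reached |
| Dose 3 10/18 | 8/18 = 0.444 | 0 | upper quartile 120 min, with 11/18 = 61% converted; median unchanged | upper quartile not reached |
| Dose 5 28/36 | 8/36 = 0.222 | 0 | median and quartiles unchanged; tail only | all quartiles before 90 min |

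Which statistic is affected therefore depends on S(90):
- above 0.50, the median;
- above 0.25 and up to 0.50, the upper quartile;
- at or below 0.25, only the tail.

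Two late placebo conversions, at 110 and 140 min, give 0.857 × 1/2 = 0.429 and then 0. The median becomes 110 min with 8/42 = 19% converted.

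**Log-rank test.** At an event time with one patient at risk across both arms, observed minus expected is 1 − 1 = 0 and the variance is 0. The test cannot move: for Example 1, placebo v Dose 3, chi-square is 12.03 (p = 0.0005) with or without the late placebo event. A change needs someone in the other arm still at risk after 90 min. That must be a second late converter, or an unshocked non-converter who was not censored at 90 min. With one such patient, the late event adds an expected count of 1/2 and a variance of 1/4:

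| Comparison | 90 min cut-off | Late placebo event, one Dose patient at risk | Late Dose event, one placebo patient at risk |
|---|---|---|---|
| Example 1, placebo 6/42 v Dose 3 10/18 | 12.03, p = 0.0005 | 9.32, p = 0.0023 | 13.03, p = 0.0003 |
| Example 2, placebo 8/42 v Dose 5 5/12 | 2.71, p = 0.100 | 1.51, p = 0.219 | 3.55, p = 0.060 |

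None of these crosses 0.05.

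**The case against.** The best reply is that a 90 min horizon is already in the text. SAP 8.2.1 ties the median and interquartile range to patients who converted by 90 min, and 90 min is the only censoring time it gives. On that view a 120 min median would never be reported. Appendix I is only sample code, and a curve that falls to 0 with one patient at risk would look odd on the plot.

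Much of this stands. A cap was probably intended, and a reader who inferred that the SAP deliberately prescribes a distorted curve would be going too far: the late event gets in by omission. But the sentence describes a summary. It does not say how a patient who converts at 120 min is coded or when that patient is censored. The time formula and the censor definition, which a programmer would follow, contain no cap. The plot may also not be there to warn anyone at an interim, because only the table is marked for delivery.

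A reader might also infer that patients who neither convert nor receive a shock fall into the same gap. The documents do not clearly support that. Appendix I gives these patients censored status, and the 90 min censoring sentence can be read to cover them. If they are censored at 90 min, the shifted log-rank results above require a second late converter, in the other arm.

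**Conclusion.** The point holds as a gap in the censoring rule of one secondary analysis. Under the literal rule, one unshocked conversion after 90 min can turn a not-reached placebo median into 120 min with 17% converted, or supply an upper quartile that a 10/18 arm did not reach. This rests on the example counts, an assumed conversion at 120 min, and nobody else in the arm being at risk then.

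Two stronger readings are not supported:
- **The treatment comparison is compromised.** The log-rank test is unchanged when the late converter is alone at risk, and no scenario tested crossed 0.05.
- **The event is likely.** The documents give no late-conversion rate. Among 36 patients still in AF, the chance of at least one is 1 − (1 − q)^36. That is 17% for an assumed q of 0.5% and 84% for 5%, a range too wide to support any claim about frequency.

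The primary Bayesian analysis, the dose rule and the Kaplan-Meier curve up to 90 min are unaffected. Low priority.

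**What to change.** State in SAP 8.2.1, and in the Appendix I definition of the censor variable, that only conversions up to 90 min are events. All other patients are censored at 90 min, whether they are later shocked, convert later, or neither. The plot, quartiles and log-rank test then cover 0 to 90 min, and later conversions are listed.

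The cost is one sentence and one line of derivation code. The downside is that conversions after 90 min are listed and not analysed, although the endpoint has no 90 min limit.

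Censoring at the actual shock time is an alternative, but it does not close the gap by itself. In the placebo example, if all shocks come at 150 min, S after 120 min is 0.857 × 35/36 = 0.833 and the median is not reached. If all come at 100 min, the late converter is again alone at risk and the median is 120 min. The all-at-100 case is extreme: with shocks spread over 92 to 180 min (assumed), S is 0.823 and no median is reached. If the sponsor wants to keep later conversions in the analysis, treating the shock as a competing event with a common later horizon would also work (0.833 not converted, median not reached), but it needs more specification than the cut-off.
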